Using G*Power 3.1, sample sizes needed to detect group differences in the primary outcome (changes in accommodation from baseline to follow-up) between the BRAVE group and the Control group of small (.2), medium (.5), and large effects (.8) based on an F test, linear multiple

regression with $\alpha = .05$ and power = 0.80 were 395, 55, and 25, respectively for the primary outcome (hypothesis 1). The target sample of 300 (150 per SSI condition accounting for attrition) reflects power to detect a small to medium effect as observed by previous SSI trials.

Analytic Plan

To address *hypothesis 1*, a multiple linear regression with intervention condition (1=ORR+Project Brave; 0=ORR+waitlist control) and baseline accommodation levels (sum score of the first 9 items of the Family accommodation scale with higher scores indicating higher levels of accommodation) as predictor variables will indicate whether ORR+Project BRAVE, versus ORR+delayed SSI access, led to differential reductions in accommodation behavior from baseline to 2-week follow up. A p-value of $<.05$ will indicate a significant change in parental accommodation from baseline to 2-week follow up.

To address *hypothesis 2*, we will use the two-sample t-test to determine whether the difference between the ORR+project BRAVE and ORR+delayed SSI access group's mean ratings of the perceived post intervention condition change item is significant. A p-value of $<.05$ will indicate a significant difference between the two conditions. Descriptive statistics of the scores for both conditions will be reported as well with a mean rating above 3 (out of 5) indicating an overall, subjectively-detectable pre-to-post change.

To address *hypothesis 3*, we will examine mean scores on the Program Feedback Scale from the intervention group only. A score above 3 on any given program feedback scale item will reflect endorsement of that item (e.g. positive feedback/adequate acceptability). Thus, a mean score of 3 or higher (out of 5) across participants in this study will indicate participants found the intervention acceptable.

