The false discovery rate (FDR) will be applied to identify potential false-positive results. Q -values will be computed for p -values from each mixed effects linear model using an online calculator applying Benjamini and Hochberg's approach Benjamini and Hochberg's approach (1995); www.sdmproject.com/utilities/?show=FDR). Results from tests described above will be considered significant if FDR corrected $q < 0.05$.

Methodological Details Not Mentioned Elsewhere

Follow-up Period

We are intending on a 2 week follow-up period from the SSI but will allow up to 5 weeks post-intervention. Participants will be reminded once every two days for 6 days (total of 3 reminders) to complete the post-intervention questionnaires.

Operational Definition of Completion Rates for participants assigned to both conditions

Intervention completion rates for the ORR+ Project BRAVE group will be treated as a categorical (full completers, psychoeducational content completers, personalized-plan completers).

Categorical definitions of completion rates are defined as follows: full completers are all participants who reached the end of the SSI content (slide Q254), psychoeducational completers are all participants who received all of the psychoeducational content of the program (slide Q235), and personalized-plan completers are all participants who completed the step-by-step action plan for responding in a helpful way to their child's anxiety or avoidance (slide Q243)

Excluding Participants From Analysis

Participants will be excluded from analyses *only* if it is apparent from their free responses during the SSI that they are non-english speakers. If a participant completes either the baseline or

follow-up survey more than once, their *more-complete* response will be used in analysis (if responses are equally-complete, their *first* response will be used).

Differential Dropout Rates

We will assess for differential follow-up rates among full completers in each group by using Z-tests of differential proportions where we compare the proportion of people who drop out before completing the follow-up (Y or N) as a function of treatment condition (1 = ORR+Project Brave; 0 = waitlist control).

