For participants assigned to the ORR+ delayed SSI access group, a participant must have made it through all baseline measures (i.e., they must reach the final “page” of the baseline questionnaires, or the RCADS, though it is acceptable for the participant to leave the answer blank after seeing it) to be considered a “full completer”. For participants assigned to the ORR+Project BRAVE group, a participant must have made it through all of the intervention (i.e. they must reach the final “page” of the intervention) to be considered a full completer.

To be considered a follow-up “completer”, a participant must have made it through all of the questionnaires in the follow-up surveys (i.e. they must reach the final “page” of the follow-up questionnaires though it is acceptable for the participant to leave the answer blank after seeing it).

If the p value is greater than .05 we will assume dropout was not dependent on condition assignment and can proceed with interpreting the effects of intervention assignment. If the p value for this test is less than .05 we will conclude that dropout was dependent on condition assignment, and we will take the following steps to improve the interpretability of our results. Unequal dropout between treatment groups can introduce bias in trial results; however, this is not always the case (Bell, Kenward, Fairclough, & Horton, 2013; <https://doi.org/10.1136/bmj.e8668>). One major concern is that, if data is not missing at random, systematic differences may exist between “dropouts” and “completers” that cannot be corrected for, limiting the interpretability of our results. For example, if more control condition participants experienced a worsening of clinical symptoms and dropped out before completing follow-up measures, this worsening of symptoms would not be captured by completers’ data (or by data imputed based on the available completers’ data). Thus, should unequal dropout exist between conditions in the present study, we will report the results of our main analyses while highlighting (1) limitations to interpretation, and (2) ways in which this will inform future intervention development.

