Further, if unequal dropout is present, we will run a sensitivity analysis to determine a range of possible effect sizes for our outcomes of interest, varying how much “dropout participants” may have changed on each outcome. To establish lower- and upper-end estimates of effect size, we will: (1) calculate residual change for each of our 3 outcomes, (2) identify the 25th and 75th percentile values for residual change in each outcome, (3) run analyses for each outcome where we impute the lower residual change value (25th percentile) for all dropouts/missing data, as well as the higher residual change value (75th percentile) for all dropouts/missing data. This approach explicitly assumes data are not missing at random, providing a more unbiased estimate of the overall treatment effect in the presence of unequal dropout.

Exploratory Moderation Tests

We will also conduct exploratory moderation tests examining various baseline variables as moderators of the SSI's impact on outcome, using the same approaches to missing data and corrections for multiple tests as described elsewhere in the pre-registration

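### A non-significant test of dropout counts is read as no dependence on condition and switches off the caveats and the not-missing-at-random analysis, which would itself need arm-specific values to be informative

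*SAP*

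**What the plan says.** The section Differential Dropout Rates first names the population of the test: "We will assess for differential follow-up rates among full completers in each group". The method is a comparison of two dropout proportions, worded as "by using Z-tests of differential proportions where we compare the proportion of people who drop out before completing the follow-up". The decision rule for a null result is: "If the p value is greater than .05 we will assume dropout was not dependent on condition assignment and can proceed with interpreting the effects".

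If p < .05, two things follow. The main results are reported with their limitations highlighted, and "if unequal dropout is present, we will run a sensitivity analysis to determine a range of possible effect sizes for our outcomes of interest". That analysis imputes the 25th and then the 75th percentile of residual change for every dropout. The SAP describes it as explicitly assuming that data are not missing at random.

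The same section gives an example of what it fears: "if more control condition participants experienced a worsening of clinical symptoms and dropped out before completing follow-up measures, this worsening of symptoms would not be" visible in the completers' data, nor in values imputed from those completers.

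The Missing Data section always imputes with Amelia II. It mentions a sensitivity analysis beforehand, but gives neither its method nor what would follow from its result.

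**The concern.** The rule has two weaknesses.

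- It treats failure to reject equal dropout as grounds for assuming that dropout did not depend on condition. With a test of modest power, that assumption is often wrong.
- It looks at how many parents left and not at which parents left. If the arms lose similar numbers for different reasons, the test is null by construction and nothing further is done.

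In both cases the trial would report the imputed result without a sensitivity range and without the caveat. The SAP itself says that such imputation cannot see worsening among those who left. Whether the robustness of the 2-week results (accommodation and distress tolerance) is examined at all would depend on a pretest that is not suited to the question.

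**Working it through.** **Inputs.** Number per arm: "The target sample of 300 (150 per SSI condition accounting for attrition" (Sample Size Justification), so 150. This is an upper limit for the dropout test, which covers full completers only. Two-sided .05 is assumed because sidedness is not stated. Dropout rates are assumed because the SAP gives none.

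**The plan's own figures.** The SAP states no power for the dropout test. Its only power figures are for the primary outcome: "regression with $\alpha = .05$ and power = 0.80 were 395, 55, and 25". A noncentral F calculation with one tested predictor and f² = .02, .15 and .35 returns exactly 395, 55 and 25. They do not bear on the dropout test.

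**Step 1: power of the trigger.** For 20% v 30% with n = 150 per arm:

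- SE under equality = √(2 × 0.25 × 0.75 / 150) = 0.0500
- SE under the true rates = √((0.20 × 0.80 + 0.30 × 0.70) / 150) = 0.0497
- Power = Φ((0.10 − 1.96 × 0.0500) / 0.0497) = 0.516

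Exact binomial enumeration of the pooled Z-test gives 0.520, a miss rate of 48%. Exact miss rates for a true 10-point gap:

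| True dropout | 150 per arm | 120 per arm |
|---|---|---|
| 5% v 15% | 16% | 24% |
| 10% v 20% | 31% | 41% |
| 15% v 25% | 41% | 50% |
| 20% v 30% | 48% | 57% |
| 30% v 40% | 56% | 63% |
| 40% v 50% | 57% | 67% |

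For 80% power the test would need 199 per arm at 10% v 20%, 294 at 20% v 30% and 356 at 30% v 40%.

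**Step 2: what a null result can look like.** Take 45 of 150 v 61 of 150 lost. Pooled rate = 106/300 = 0.353; SE = √(0.353 × 0.647 × 2/150) = 0.0552; z = (16/150) / 0.0552 = 1.93; p = .053. The rule then assumes no dependence. The 95% interval for the gap is 10.7 ± 1.96 × 5.49 points, or −0.1 to 21.4, which is far from evidence of no difference. One more loss (62) gives p = .040 and triggers every step.

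**Step 3: equal counts, different leavers.** At 20% or 30% dropout in both arms the trigger fires 5.0% of the time, whatever the reasons for leaving. If control leavers are δ SD worse than imputed and BRAVE leavers are as imputed, the error in the group difference is rate × δ. At 30% and δ = 0.5 it is 0.30 × 0.5 = 0.15 SD. For rates of 20% to 30% and δ of 0.5 to 1, it is 0.10 to 0.30 SD. Here the control mean looks too good, so BRAVE's benefit is understated. The mirror case, BRAVE leavers who did worse than imputed, would overstate it by the same amount.

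**Step 4: would the existing sensitivity analysis show this if always run?** Take Step 3 with an assumed difference of −0.30 SD among stayers (lower is better). The true difference is −0.30 − 0.15 = −0.45. A common value c given to all dropouts adds 0.30 × c to each arm and cancels. With residuals taken from a regression on baseline alone, the estimate is 0.70 × (−0.30) = −0.21 whether c is the 25th or the 75th percentile; a simulation gave −0.21 at both ends. If condition is in the residual model, both ends are −0.30. Either way the range has no width and excludes −0.45.

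Let the value differ by arm, assuming normal residuals with SD 1 (quartiles ±0.67). The two crossed choices give −0.21 ± 0.30 × 2 × 0.67 = −0.21 ± 0.40, or −0.61 to +0.19, which includes −0.45.

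**The case against.** Several points on the other side have force.

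- **The test does address the plan's own example.** That example has more controls leaving, so a count imbalance is what it would produce. At low dropout the trigger works fairly well, firing 84% of the time at 5% v 15% and 69% at 10% v 20%. This stands, and a reader should not infer that the rule would usually fail in the scenario the SAP describes. The equal-count case is a further situation that the SAP does not discuss.
- **No dropout rate is given.** A reader might infer that the test misses a 10-point gap about half the time as a general property. That holds only for assumed lower-arm rates of roughly 15% or more.
- **The threat is not ranked first.** The SAP offers worsened controls as an example of one major concern, and calling it the main threat would go beyond the text.
- **There is another missing-data check.** The one in Missing Data is not gated, but it is undefined and has no stated consequence. It yields neither a range of effects nor a caveat, so it does not fill the gap.
- **Simply running the existing analysis every time would not help with equal counts.** This is right, as Step 4 shows: it could reassure falsely. It bears on the remedy and is no argument for the gate. With unequal dropout the common value does have some width: for a 10-point gap, 0.10 × 1.35 = 0.13 SD under the same normal assumption.

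**Conclusion.** The rule should be changed. A p value above .05 in a comparison of dropout counts does not support the assumption drawn from it, and should not decide whether limitations and a not-missing-at-random analysis are reported. At 150 per arm the exact miss rate for a true 10-point gap runs from about 16% to 57% over the assumed rates, and it is higher with fewer full completers. With equal counts the trigger is uninformative, and an error of 0.15 SD (30% dropout, 0.5 SD shift in one arm) would pass unexamined. The dropout rates and the shift are assumptions.

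A reader might infer that the trial is exposed to a false positive or that its primary analysis is invalid. The document does not support that. In the SAP's own example the bias understates BRAVE's benefit, and the primary regression stands. What is lost is a dependable check on its robustness.

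**What to change.** In Differential Dropout Rates:

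1. Delete the sentence that assumes no dependence when p > .05, and both conditions that tie further steps to unequal dropout.
2. Report follow-up loss by arm for all randomised parents, with the difference and its 95% confidence interval, and the baseline scores of leavers and completers by arm. All randomised parents are needed because full completion is defined differently in the two arms and occurs after assignment.
3. Run and report the not-missing-at-random analysis for the 2-week outcomes whatever the size or p value of the difference.
4. Let the imputed value differ by arm: for example the 25th percentile in one arm with the 75th in the other, and the reverse, or a grid of arm-specific shifts. State whether residual change is computed with or without condition in the model.

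The cost is SAP wording and a few more analyses of data already collected. The downside is that a sensitivity range, possibly a wide one, will always accompany the main result, even when dropout looks balanced.

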Empowering Anxious Parents to Manage Child Avoidance Behaviors: A Randomized Trial of a Single-Session Intervention Targeting Parent Accommodation (Project BRAVE)

Hypotheses, Aims, and Analytic Plan
August 31, 2020

Study Timeline

Recruitment is projected to begin in July 2020 and extend through approximately June 2021.

NOTE: This analytic plan was developed prior to the study's lead authors ([name], [name]) downloading, seeing, or using any of the data collected as part of this trial. Similarly, other exploratory analysis will be pre-registered at a later date under the same conditions.

Study Aims and Hypotheses

The primary goals of the study will be as follows:

1. Examine the SSI's (ORR+Project BRAVE) direct effects on parental accommodation, relative to an information-only control (ORR+delayed SSI) at two weeks follow-up.
2. To assess whether parents' perceive their ability to help their child manage distress as *improved* immediately following the completion of the active SSI (ORR+Project BRAVE), compared to an information-only control (ORR+delayed SSI).
3. Evaluate the SSI's acceptability, per self-report ratings.
4. To assess whether parents' distress tolerance improves in the active SSI (ORR+Project BRAVE) condition versus the information-only control (ORR+delayed SSI) group at two weeks follow-up.

Hypotheses associated with each of these primary aims will be as follows:

1. Parental accommodation of child anxiety will decrease significantly more among parents assigned to the ORR+Project BRAVE group, relative to parents assigned to the ORR+waitlist group from baseline to 2-week follow-up
2. Relative to parents who receive ORR, parents who receive Project BRAVE will be more likely to perceive increases in their preparedness to cope with their child's distress from before to after completing their baseline session.
3. Participants assigned to the Intervention Group will find Project BRAVE to be acceptable, indicated by a mean score of > 3 (out of 5) across Program Feedback Scale items (completed by parents assigned to the intervention group at immediate post-intervention).
4. Parents' self-reported distress tolerance will decrease significantly more among parents in the ORR+Project BRAVE group relative to those ORR+waitlist group from baseline to 2-week follow-up

Sample Size Justification

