To address *hypothesis 4*, a multiple linear regression with intervention condition (1=ORR+Project Brave; 0= ORR+waitlist control) and baseline parental distress in the context of child negative affect as predictor variables will indicate whether ORR+Project BRAVE versus ORR+delayed SSI led to greater reductions in parental distress from baseline to 2-week follow up. Parental distress will be indicated by the sum score of the distress tolerance scale. A p-value of $<.05$ will indicate a significant change in parental distress in the context of child negative affect from baseline to 2-week follow up.

Testing Assumptions

To justify the use of linear regression models for the purpose of prediction, we will check the following principle assumptions: 1) linearity and additivity of the relationship between dependent and independent variables, 2) statistical independence of the errors, 3) homoscedasticity of the errors, 4) normality of the error distribution. Nonlinearity will be tested by checking for a symmetric distribution of points on a plot of observed versus predictive values or residual versus predicted values. To check statistical independence of the errors, residual autocorrelations will be plotted to identify values that fall outside the 95% confidence band around zero. Homoscedasticity will be checked by plotting the residuals versus the predicted

values to examine the distribution of residual scores. Finally, normally distributed errors will be checked via normal probability plot to measure skewness and kurtosis.

Missing Data

We will impute any missing data using the expectation-maximization and bootstrapping algorithm implemented with Amelia II in R after running a sensitivity analysis to ensure that data is not missing at random. These imputed datasets allow for more conservative intent-to-treat analyses than listwise deletion or last-observation carried forward. We plan to impute as many datasets as there are percent of missing data for an outcome – rounding up to the next highest percentage (e.g., If 2.4% of data is missing on an outcome, we will create 3 imputed datasets). This process will allow us to retain high power even in the presence of missing data. Cohen's d effect sizes and 95% confidence intervals for analyses will be calculated using t -values for the treatment effects obtained from the analyses with the MOTE package in R.

False Discovery Rate

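### The dropout sensitivity analysis asks for residual change on three unnamed outcomes when only two allow it, and its trigger test does not count parents who leave during the session

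*SAP*

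**What the plan says.** Under Differential Dropout Rates, the SAP compares dropout between arms with a Z-test among full completers of the session: "we compare the proportion of people who drop out before completing the follow-up (Y or N". A BRAVE parent is a full completer on reaching the last page of the intervention; a control parent, on reaching the last page of the baseline questionnaires. If p exceeds .05, the SAP takes dropout to be unrelated to arm. If p is below .05, a sensitivity analysis follows. Its first step is to "calculate residual change for each of our 3 outcomes". It then takes the 25th and 75th percentiles of those values and runs analyses where "we impute the lower residual change value (25th percentile) for all dropouts/missing data", and again with the 75th. The three outcomes are not listed.

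The Analytic Plan describes four outcomes:

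- Hypothesis 1 is a regression adjusted for baseline, asking whether the program "led to differential reductions in accommodation behavior from baseline to 2-week follow up".
- Hypothesis 4 has the same form, asking whether it "led to greater reductions in parental distress from baseline to 2-week follow up".
- Hypothesis 2 is a two-sample t-test of whether the difference between the arms' "mean ratings of the perceived post intervention condition change item is significant". There is no baseline covariate, and the hypothesis places the change "from before to after completing their baseline session".
- For hypothesis 3, "we will examine mean scores on the Program Feedback Scale from the intervention group only".

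Under Missing Data, all missing values are to be imputed with Amelia II.

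**The concern.** Residual change is what remains of a follow-up value after regression on the baseline value of the same measure. An outcome rated once has no such quantity. If the third outcome is the perceived-change item, the analyst meets an instruction that cannot be followed and must either drop the item or improvise a method, with the data already in hand.

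The trigger has a related gap. The perceived-change rating is given around the end of the session, so the natural way to lose it is to leave during the session. The trigger is restricted to parents who finished, so in the BRAVE arm it leaves out those who left the program early. A null result would then be read as dropout unrelated to arm, although loss within the session had not been examined. The perceived-change comparison is listed among the study's primary aims, so its robustness to informative loss matters.

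**Working it through.** **Step 1: which outcomes allow residual change.** The time points come from the Study Aims and Hypotheses and the Analytic Plan.

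| Outcome | Baseline value | Later value | Compared between arms | Residual change defined |
|---|---|---|---|---|
| H1 accommodation | yes | 2 weeks | yes | yes |
| H2 perceived change | none stated | after session | yes | no |
| H3 program feedback | none stated | after session | no, BRAVE only | no |
| H4 distress tolerance | yes | 2 weeks | yes | yes |

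Two outcomes have both values, against the stated 3. The figure 3 is reached as the number of between-arm tests (H1, H2, H4), which brings in H2. Choosing H3 instead does not help, since it has neither a baseline nor a control arm. The RCADS appears only as a baseline questionnaire, with no hypothesis attached. No set of three from the stated hypotheses makes the rule executable.

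**Step 2: what the trigger measures.** Let s be the proportion of an arm that leaves during the session, and f the proportion of those who finish it that is then lost before follow-up. Subscripts B and C denote BRAVE and control.

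- The trigger compares f_B with f_C.
- If leaving the session is what removes the H2 rating, H2 missingness differs by s_B − s_C.
- If session leavers also skip the follow-up, loss for H1 and H4 in each arm is s + (1 − s)f. With f equal in both arms, the arms differ by (s_B − s_C)(1 − f).

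When f is equal, the trigger sees no difference, whatever the value of s_B − s_C. Missingness can then differ by arm for H2, and also for H1 and H4. Conversely, a parent who gave the H2 rating but skipped the follow-up counts as a dropout although no H2 value is missing. Session leavers are not removed from the analysis: the SAP excludes only parents whose free responses show that they do not speak English.

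**Step 3: possible size for H2.** In each arm, mean over all parents = stayer mean − (loss) × (gap), where gap = stayer mean − leaver mean. With the same gap in both arms:

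observed difference − difference over all parents = (loss in BRAVE − loss in control) × gap

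The SAP gives no loss rates and no gap, so every input here is assumed:

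| Loss difference | Gap 0.5 point | Gap 1 point |
|---|---|---|
| 10 percentage points | 0.10 × 0.5 = 0.05 | 0.10 × 1 = 0.10 |
| 20 percentage points | 0.20 × 0.5 = 0.10 | 0.20 × 1 = 0.20 |

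The range is 0.05 to 0.20 points on the 5-point item. If BRAVE loses more parents and leavers would rate lower, the observed difference overstates the effect. If either sign is reversed, it understates it.

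**The case against.** The SAP never names the three outcomes. If the analysis was meant only for outcomes measured at follow-up, the trigger fits that purpose apart from its restriction to full completers, and the slip is in the count. This stands: H2 as the third outcome is an inference. The count is wrong on any reading, however.

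A reader might infer that H2 has no protection against missing data. The SAP does not support that, because Amelia II is to impute all missing values, which includes this rating. What remains is narrower. The section on unequal dropout says that worsening among those who leave would not be captured by data imputed from completers, and the percentile analysis is its remedy for that. The remedy is undefined for H2.

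A reader might also see the trigger gap as peculiar to H2. It is not, since the restriction to full completers applies equally to H1 and H4.

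The item is itself a rating of change, so using percentiles of the raw rating is an obvious adaptation. That is fair, but the SAP does not specify it.

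It is tempting to set the illustrated bias against the SAP's small effect of .2. That figure belongs to the accommodation analysis, and the SAP gives no standard deviation for the H2 item, so the comparison is not supported.

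Finally, the sensitivity analysis is secondary and conditional, and it can still be run for accommodation, which the sample-size section calls the primary outcome. This limits the consequence.

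**Conclusion.** The point holds in a limited form. The SAP asks for residual change on three outcomes where its own design supplies two. For the likely third, the perceived-change item, the only check that assumes data are not missing at random cannot be run as written. Separately, the trigger leaves out parents who leave during the session, so it can be null while missingness differs by arm for any of the three between-arm outcomes.

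No main analysis is invalidated, and the check remains available for hypotheses 1 and 4 once triggered. The document does not show that loss within the session will differ by arm. That is plausible, since the SAP defines graded completion categories for BRAVE and so expects some parents to stop partway, but the position of the rating in the session is not stated. The range of 0.05 to 0.20 points is an illustration. It rests on assumed loss differences and gaps and on an equal gap in both arms.

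**What to change.** 1. Name accommodation and distress tolerance as the outcomes for the residual-change analysis, in place of the count of three.
2. Compare missingness of each between-arm outcome by arm among all randomised parents, not only full completers, and base the trigger on that comparison.
3. For the perceived-change item, report a sensitivity range on the raw 1-5 rating. Impute a low and then a high value for missing ratings, for example the 25th and 75th percentiles. On a 5-point item these may coincide, so state a fixed point shift to use in that case. Include a scenario in which the imputed values differ by arm, since imputing the same value in both arms would not show the effect of leavers who differ by arm. Describe the result as a range and not as bounds, because quartiles do not limit what the missing ratings could be.

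The cost is a few sentences in the SAP and one or two extra sensitivity runs. The hypothesis 2 result may look less certain.

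### The dropout sensitivity analysis moves both arms the same way, so the width of its range follows the gap between the arms' missing fractions and no run covers arm-specific dropout

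*SAP*

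**What the plan says.** Under Differential Dropout Rates, the SAP compares dropout between arms with a Z-test. If p is below .05, a sensitivity analysis follows, introduced as "To establish lower- and upper-end estimates of effect size". Residual change is calculated for each of three outcomes. The next step is to "identify the 25th and 75th percentile values for residual change in each outcome", and then to "run analyses for each outcome where we impute the lower residual change value (25th percentile) for all dropouts/missing data". A second run does the same with the 75th percentile. No run, here or elsewhere in the SAP, gives the two arms different percentiles. The SAP does not say whether the percentiles are pooled or taken within arm. It describes the approach as assuming data not missing at random and as "providing a more unbiased estimate of the overall treatment effect in the presence of unequal dropout".

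Three other statements bear on this:

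- The same section motivates the step with the example "if more control condition participants experienced a worsening of clinical symptoms and dropped out before completing follow-up measures".
- The triggering test has a restricted population: "We will assess for differential follow-up rates among full completers in each group by using Z-tests of differential proportions". To be a full completer in the BRAVE arm, "a participant must have made it through all of the intervention"; in control it is enough to reach the last page of the baseline questionnaires. The imputation covers everyone with missing data.
- Under Missing Data, results are put on the Cohen's d scale: "effect sizes and 95% confidence intervals for analyses will be calculated using t -values for the treatment effects".

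**The concern.** When dropout differs by arm, the worry is that the missing parents in one arm did differently from the missing parents in the other. Giving all of them the same good value, then the same poor value, does not examine that. Most of the imputed value cancels in the between-arm comparison, and what remains depends on how unequal the missing fractions are. A trial with heavy but similar losses in both arms would then show a narrow range, which could be read as robustness to dropout when it shows only that the missing fractions are close.

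**Working it through.** The SAP gives no figure for this range and no expected dropout rates, so there is no printed result to reproduce. From the SAP: 150 per arm, a regression on condition and baseline, and the 25th and 75th percentiles. Assumed: true effect -0.32 SD, baseline correlation .6 (residual SD 0.8, so d = -0.32/0.8 = -0.40), normal residuals, and the missing fractions shown. Estimates described as simulated come from 1,000 or more replicates per setting.

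**1. Algebra.** Let m1 and m0 be the fractions missing in BRAVE and control, mu1 and mu0 the completers' mean residuals, and c the common imputed value:

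effect(c) = (1 - m1)mu1 - (1 - m0)mu0 + (m1 - m0)c

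The two planned runs therefore differ by |m1 - m0| x IQR. With within-arm percentiles the difference is |m1 x IQR1 - m0 x IQR0|, nearly the same when the spreads are similar. With opposite percentiles in the two arms, then swapped, the difference is (m1 + m0) x IQR.

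**2. Width.** Pooled residual SD = sqrt(0.64 + 0.32²/4) = 0.816, and IQR = 1.349 x 0.816 = 1.101 SD.

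| Missing, BRAVE v control | Planned width | Opposite-direction width |
|---|---|---|
| 30% v 20% | 0.10 x 1.101 = 0.110 | 0.50 x 1.101 = 0.550 |
| 35% v 20% | 0.15 x 1.101 = 0.165 | 0.55 x 1.101 = 0.605 |

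If all 150 per arm enter the test, 45 v 30 dropouts (30% v 20%) give z = 0.10/0.05 = 2.00, so the first row only just triggers the step. At a fixed 10-point gap the planned width is the same whether 20% v 10% or 60% v 50% are missing: 0.135 in residual-SD units.

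**3. What total missingness does change.** With pooled percentiles, heavier loss pulls the range toward zero. For an assumed effect of -0.3 residual SD, the midpoint is -0.255 at 20% v 10% and -0.135 at 60% v 50%. On the t-based d scale the width also rises somewhat, from 0.146 to 0.181, because constant imputation shrinks the residual variance.

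**4. Does the range reach the assumed truth of -0.32?** Simulated; missing fractions are 35% and 20%. A log-weight of 0.5 means that the relative weight for dropping out rises by e^0.5 = 1.65 per residual SD of worsening.

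| Dropout process | Planned, pooled | Planned, by arm | Reaches -0.32? |
|---|---|---|---|
| Random, BRAVE loses more | -0.31 to -0.15 | -0.40 to -0.25 | nearly; contains |
| Worsening in control only, control loses more, 0.5 | far end -0.19 | far end -0.23 | no; no |
| Same, 1.0 | far end -0.11 | far end -0.11 | no; no |
| Worsening in both arms, control loses more, 0.5 | -0.26 to -0.10 | -0.32 to -0.18 | nearly; just |
| Worsening in both arms, BRAVE loses more, 0.5 | -0.36 to -0.21 | -0.47 to -0.32 | contains; just |

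In the two control-only rows the missing-at-random estimates are -0.16 and -0.05. An opposite-direction run made as a shift on the imputed values gives -0.45 and -0.32.

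**5. Tested v imputed fractions.** A constructed case: 30 of 150 BRAVE parents do not finish the intervention and do not return, 24 of the other 120 drop out, and 54 of 150 controls drop out. The test sees 24/120 = 20% v 54/150 = 36% (z = 2.88), so the step is triggered. The imputed fractions are (30 + 24)/150 = 36% and 54/150 = 36%, and the two pooled runs coincide at 0.64 x -0.32 = -0.205.

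**The case against.** The plan's logic suits one reading of its own example. If worsening drives dropout in both arms but is commoner in control, a common poor value with unequal fractions is a reasonable device. The SAP promises a range, commits to highlighting limitations, and rests no decision on the step. All of this stands and limits the severity.

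Four stronger inferences are tempting and are not supported:

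- *The range usually misses the truth.* It misses under control-only worsening; in the other settings tried it nearly reaches, just reaches or contains it.
- *The step is no better than the main analysis.* When control loses more, the worse-side run equals or improves on the missing-at-random estimate: -0.19 v -0.16 under control-only worsening, and about -0.25 v -0.25 (pooled) under worsening in both arms. The SAP's claim of less bias is still too strong, since the other run lies further away and the SAP does not choose between them.
- *The amount missing does not matter.* That is exact only for the width on the coefficient scale. The location moves, and so, modestly, does the width in d.
- *The two runs will coincide in practice.* The 36% v 36% case was built to do so. It needs exact equality and pooled percentiles, no return of BRAVE non-finishers, and no control left out of the test, although the control completion rule could exclude some. It shows only that the tested gap does not fix the width.

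**Conclusion.** The concern holds in a limited form. The planned runs differ by |m1 - m0| x IQR on the coefficient scale, and none lets dropouts differ in direction by arm. The range therefore does not cover control-only worsening, which is one reading of the SAP's own motivating example. The width formula is algebra under pooled percentiles and nearly holds by arm; every SD value rests on the assumed effect, correlation, dropout rates and dropout weights. Severity is minor to moderate: the step is conditional and supplementary, but nothing else in the SAP fills the gap, and the claim of a less biased estimate should not stand as written.

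**What to change.** 1. Keep the two same-direction runs and add two opposite-direction runs: BRAVE dropouts shifted by the 25th-percentile residual with control dropouts by the 75th, and the reverse. Apply the percentiles as shifts added to the Amelia II draws, with condition in the imputation model, and combine across imputations.
2. If a run that worsens only control dropouts is added, add its mirror for BRAVE dropouts. Alone it favours BRAVE: under random dropout at 35% v 20% it gives about -0.42 when the truth is -0.32.
3. State whether percentiles are pooled across arms or taken by arm.
4. Report the coefficient beside Cohen's d, with the missing fraction in each arm among all analysed participants, not only among full completers.
5. Replace the claim of a less biased estimate with a statement that the results are a sensitivity range under stated departures from missing at random, and are not bounds.

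The cost is wording and a few more runs per outcome, with no new data. The range becomes wider (about 0.60 v 0.16 SD at 35% v 20%), so conclusions under unequal dropout will be less firm. Cohen's d from combined t-values is pulled toward zero (about -0.34 for a true -0.40 at 35% v 20%), which is why the coefficient is needed beside it.
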